14.2 Demographic and Baseline Characteristics

The PAIN and NO PAIN groups will be compared on all matching variables (methadone dose, cigarettes smoked per day, annual income, years of education, and age) using t-tests and chi-square tests as appropriate. If statistically significant differences are detected despite efforts to match during recruitment, matching variables will be included as covariates in subsequent analyses. It is recognized that this method is inferior to formal matching; therefore, substantial effort will be devoted to locating appropriately matched individuals. Measures obtained at 15-minute intervals during each session (pain, vital signs, opioid withdrawal, etc.) will be examined in terms of group comparability and to

Version #: 1.9 Version Date: 12/09/2020 Page 24 of 37

confirm that naloxone precipitated withdrawal symptoms compared to placebo. All psychometric, scaled measures will be scored according to standardized algorithms and internal consistency reliability examined. Given the design of the study, unit level missing data is not anticipated. Item level missing data will be minimized through supervised administration of measures. Missing data patterns will be examined and multiple imputation (SAS PROC MI) or other strategies employed as appropriate. Using methods developed by co-I [name], nonlinear regression will be used to calculate individual values of k, larger k values indicate greater discounting or more impulsiveness. K values are normalized using log transformation for parametric analysis (45).

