4 STUDY DESIGN

4.1 Study Overview

This is an outpatient Phase 1 clinical trial investigating the effect of naloxone precipitated withdrawal on delay discounting. Eligible participants will undergo two experimental sessions presented in random order. One session will involve the measurement of delay discounting 30 minutes after double-blind intramuscular (IM) administration of placebo (normal saline) and the other will have the exact same procedures performed after double-blind IM administration of naloxone (0.1 mg). Injections will occur 2 hours after methadone dosing (peak levels). Study sessions will last 2 hours and involve pain and opioid withdrawal measures assessed at baseline and 15-minute intervals after injections. Sessions will occur at least 48 hours apart.

This is a two-year grant proposal. The first two months will be used for study start-up, the next 20 months for study recruitment and completion of all study visits, and the last two months for data analysis and manuscript preparation. Each participant is expected to participate for 2-4 weeks, depending on scheduling of two sessions.

There are three sites on the campus of Zuckerberg San Francisco General Hospital where activities will take place. (1) Opiate Treatment Outpatient Program (OTOP). Participant recruitment, data collection and storage, and some study visits will take place at OTOP. (2) Unit 5B in Building 5. ECGs during screening and unblinded study medication preparation. (3) Ward 84 in Building 80. Some study sessions may take place at Ward 84. Johns Hopkins University's Behavioral Pharmacology Research Unit (BPRU) will be the site of data analysis. Johns Hopkins will only have access to de-identified human subject data, and so a central IRB is not needed for this study.

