8 STUDY MEDICATIONS

8.1 Method of Assigning Subjects to PAIN or NO PAIN Groups

Patients with chronic pain will be identified by self-report and confirmed by history and physical performed by [name] or another qualified study clinician. Pain will be assessed using the miscellaneous pain questionnaire from the National Health and Nutrition Examination Survey (NHANES; (83)), the Widespread Pain Index, and the Brief Pain Inventory. [name] will be consulted on challenging cases to help clarify the presence or absence of chronic pain.

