9.1.2 Demographics

Demographic information (date of birth, gender, race) will be recorded at Screening.

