14.4 Analysis of Secondary Endpoints

First, general linear model analyses (SAS PROC GLM) will be conducted to independently examine the impact of Condition and Pain Catastrophizing (PCS) on discounting rate (k). Then, a single GLM analysis will be conducted that includes Condition, PCS, and the Condition–by-PCS interaction. A significant interaction will indicate effect modification. We will also examine the effect of biological sex on discounting, opioid withdrawal, pain VAS, and pain catastrophizing. Based on prior research, we expect females to have higher PCS scores. We will also explore how the type of chronic pain (musculoskeletal, neuropathic, mixed/other) will effect discounting. We will also explore associations between somatization (SCL-90), depression (PHQ-9) and anxiety (GAD-7) and discounting. ng.

Safety and tolerability data will be summarized by study medication.

Adverse event rates will be coded by body system and MedDra classification term. Adverse events will be tabulated by study medication and will include the number of patients for whom the event occurred, the rate of occurrence, and the severity and relationship to study drug.

Version #: 1.9 Version Date: 12/09/2020 Page 25 of 37

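### Sex is absent from the matching list and from the 14.3 and 14.4 models, so a sex imbalance between the non-randomised PAIN and NO PAIN groups could bias the Group effect

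*Combined protocol and SAP*

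**What the plan says.** Group membership follows pain status. Section 8.1 states: "Patients with chronic pain will be identified by self-report and confirmed by history and physical". What is randomised is the order of the sessions; in section 4.1, "Eligible participants will undergo two experimental sessions presented in random order". One of the two primary hypotheses in 14.3 is that the PAIN group discounts more steeply than the NO PAIN group.

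Control of that comparison rests on section 14.2. The groups are to be "compared on all matching variables (methadone dose, cigarettes smoked per day, annual income, years of education, and age". The method given for this check is "using t-tests and chi-square tests as appropriate". The covariate rule is: "If statistically significant differences are detected despite efforts to match during recruitment, matching variables will be included as covariates in subsequent analyses". No other covariate is named. The 14.3 model contains Group, Condition and their interaction. The final model for catastrophizing in 14.4 contains Condition, the Pain Catastrophizing Scale (PCS) score and their interaction.

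Sex appears elsewhere. The synopsis lists its effect as a secondary objective, and 14.4 repeats this: "We will also examine the effect of biological sex on discounting, opioid withdrawal, pain VAS, and pain catastrophizing". It adds: "Based on prior research, we expect females to have higher PCS scores". Both sexes are eligible (6.2), with no quota or stratification. On data collection, 9.1.2 reads: "Demographic information (date of birth, gender, race) will be recorded at Screening".

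**The concern.** A contrast that is not randomised is only as good as its matching and adjustment. The plan picks five variables for that purpose and leaves out one that it treats elsewhere as a possible influence on the same outcome. The separate sex analysis in 14.4 would estimate a sex effect, but as written it does not remove sex from the Group effect. Sex precedes chronic pain and cannot be a consequence of it, so adjusting for it carries no risk of removing part of the effect of interest.

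At stake is the Group main effect. A second route exists if sex also changes the response to naloxone. A sex imbalance would then enter Group x Condition, and the expected link between sex and PCS would let part of the sex difference enter Condition-by-PCS, which 14.4 says it will read as effect modification.

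**Working it through.** **1. The plan's own figure.** Inputs: f² = 0.08 between groups and 0.02 within subjects (14.6); correlation 0.5, 100 completers (50 per group) and two-sided alpha 0.05 (synopsis, rationale for number of subjects); two sessions. Power comes from the noncentral F distribution with 1 and 98 df.

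- Between groups: λ = 0.08 × 100 × 2 / (1 + 0.5) = 10.67, power 89.9%.
- Within subjects and interaction: λ = 0.02 × 100 × 2 / (1 − 0.5) = 8.0, power 79.97%.

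The stated figure of more than 80% is reproduced to rounding (the last two sit at 80%). No stated number is in dispute.

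**2. The planned group difference in SD units.** For two equal groups, d = 2 × √0.08 = 0.566.

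**3. Possible bias.** If sex is left out, the bias in the Group effect is (difference in proportion female) × (sex effect on log k in SD). Neither factor is in the documents, so both are assumed: gaps of 10 to 30 points and sex effects of 0.2 to 0.5 SD. To get the type I error, put a bias b into f² = (b/2)² and λ = f² × 200 / 1.5. For b = 0.06, f² = 0.0009 and λ = 0.12.

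| Sex gap | Sex effect (SD) | Bias (SD) | Share of 0.566 | Two-sided type I error |
|---|---|---|---|---|
| 10 points | 0.2 | 0.02 | 3.5% | 5.1% |
| 10 points | 0.5 | 0.05 | 8.8% | 5.9% |
| 20 points | 0.2 | 0.04 | 7.1% | 5.6% |
| 20 points | 0.3 | 0.06 | 10.6% | 6.4% |
| 20 points | 0.5 | 0.10 | 17.7% | 8.8% |
| 30 points | 0.2 | 0.06 | 10.6% | 6.4% |
| 30 points | 0.5 | 0.15 | 26.5% | 13.8% |

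The formula uses the raw gap. If some of the five listed variables are in the model, the gap that matters is the one left after conditioning on them.

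**4. Which effects are exposed.** Each participant supplies both sessions, so sex cancels from the Condition main effect. A sex main effect also cancels from Group x Condition. That interaction is biased only by a sex x Condition effect, by (sex gap) × (sex difference in naloxone response). For Condition-by-PCS, the part that leaks in is the sex difference in response multiplied by the slope of sex on PCS, so it is partial. The documents give no figure for either, and none is computed here.

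**5. Would adding sex to the existing rule be enough?** With 50 per group, a significance test would detect a 40% versus 60% imbalance about 52% of the time, and 40% versus 50% about 17% of the time. A 20-point gap would go unadjusted in about half of such trials.

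**6. Power after always adjusting.** Multiply λ by (1 − R²), where R² is the squared correlation of sex with group, and use 97 df. No credit is taken for variance that sex explains.

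| Sex mix | R² | Group, λ = 10.67 × (1 − R²) | Group x Condition with sex x Condition, λ = 8.0 × (1 − R²) |
|---|---|---|---|
| balanced | 0 | 89.9% | 80.0% |
| 40% v 60% | 0.04 | 88.7% | 78.3% |
| 35% v 65% | 0.09 | 87.0% | 76.2% |
| 30% v 70% | 0.16 | 84.2% | 72.8% |

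**The case against.** The strongest reply is that confounding has not been shown. Bias needs both a sex imbalance and a sex effect on log k. The documents predict a sex effect only on PCS; for discounting they plan to look, with no direction or size. The illustrated bias is modest, the 26.5% figure needs the top of both assumed ranges at once, and the bias could mask a group difference as easily as create one. All of this stands, and it is why the point is conditional. A reader might infer that the Group effect is confounded; the documents support only that it could be.

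A reader might also infer from 9.1.2, which lists gender rather than sex, that the data for a sex analysis are missing. They do not appear to be. Section 6.2 enrols male and female adults, and 9.2.1, 10.1 and 10.2 require pregnancy testing in female subjects, so the site must already make this classification.

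A third tempting inference is that any sex difference in response to naloxone would show up as Condition-by-PCS. Only part would, in proportion to how strongly sex and PCS are related, and no such difference is predicted.

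Finally, section 14 promises a detailed SAP before the final analysis, and the sex analysis in 14.4 has no stated model, so Group might be added there. Both are openings for the fix; neither supplies it. The mention of chi-square tests beside five naturally numeric variables may hint that a categorical variable was meant to be listed, but that is a guess. Whether covariates should depend on a significance test at all is a separate question affecting all five listed variables, and it adds no weight here.

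**Conclusion.** The omission is plain in the text: a primary contrast that is not randomised has no provision for sex in matching or modelling, although the protocol treats sex as a factor worth studying for the same outcome. The consequence is possible bias, not demonstrated bias. Under assumed inputs it runs from 0.02 to 0.15 SD (about 4% to 27% of the planned difference), with 0.06 SD and a type I error of about 6.4% in the middle case and little effect at a 10-point gap. The direction is unknown. The Condition main effect is unaffected; Group x Condition and Condition-by-PCS are exposed only if sex modifies the response to naloxone, and then the PCS term only in part. The case for acting is that adjustment costs very little and guards one of the two primary hypotheses.

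**What to change.** In the SAP, and in 14.2 to 14.4:

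- Prespecify sex, using the sex/gender item already recorded at screening, as a covariate in the 14.3 PROC MIXED model regardless of any baseline test.
- Include sex x Condition when Group x Condition is interpreted, since only that term protects the interaction.
- Add sex and sex x Condition to the 14.4 PCS model.
- Report the models without sex as a sensitivity analysis.

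Matching on sex during recruitment is optional.

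The cost is one or two degrees of freedom, with no new data collection and no change in sample size. Between-group power stays between 84.2% and 89.9% across the imbalances examined. Sex x Condition costs the interaction test a little more: from 80.0% when balanced to 78.3% at 40% versus 60%, and 72.8% at 30% versus 70%.

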14 STATISTICAL METHODS AND CONSIDERATIONS

Prior to the analysis of the final study data, a detailed Statistical Analysis Plan (SAP) will be written describing all analyses that will be performed. The SAP will contain any modifications to the analysis plan described below.

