14.3 Analysis of Primary Endpoint

The primary hypotheses are that participants with chronic pain (PAIN) are more impulsive (larger k values) than participants without pain (NO PAIN) and that, within the same individual, k values will be larger in the naloxone-precipitated opioid withdrawal session compared to placebo. We will test these hypotheses using repeated measures analyses implemented in SAS PROC MIXED. The dependent variable is k (discounting). Independent variables include Group (PAIN vs. NO PAIN), a fixed, between-subjects effect and Condition (control vs. withdrawal), a repeated, within-subjects effect. The Group x Condition interaction will be examined to determine if group differences vary by condition. Planned contrasts will explore additive effects of chronic pain and withdrawal by examining whether discounting by the PAIN group in the withdrawal condition is greater than 1) discounting by the PAIN group in the control condition, or 2) discounting by the NO PAIN group in the withdrawal condition. To examine the effect of differing levels of peak aversive stimuli on discounting, we will conduct analyses using only data from the naloxone-precipitated withdrawal session that include peak COWS scores.

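### Adjustment of the non-randomised PAIN versus NO PAIN comparison should not depend on whether baseline tests are significant

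*Combined protocol and SAP*

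**What the plan says.** Section 8.1 defines the groups by clinical status: "Patients with chronic pain will be identified by self-report and confirmed by history and physical". What is randomised is session order (section 4.1): "Eligible participants will undergo two experimental sessions presented in random order".

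Section 14.3 makes larger k in PAIN than in NO PAIN a primary hypothesis, beside the within-person effect of withdrawal. Of the model it says "Independent variables include Group (PAIN vs. NO PAIN), a fixed, between-subjects effect". Condition and the Group by Condition interaction complete it, and no covariate is listed. A planned contrast also sets PAIN in withdrawal against "discounting by the NO PAIN group in the withdrawal condition".

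Covariates appear only in section 14.2. The groups are compared on methadone dose, cigarettes per day, annual income, years of education and age by t-tests or chi-square tests, and then: "If statistically significant differences are detected despite efforts to match during recruitment, matching variables will be included as covariates in subsequent analyses". The section concedes a limitation: "It is recognized that this method is inferior to formal matching; therefore, substantial effort will be devoted to locating appropriately matched individuals". It gives no matching ratio, tolerance or significance level for the baseline tests. Section 14 says that before the final analysis "a detailed Statistical Analysis Plan (SAP) will be written describing all analyses that will be performed". That later document is not part of what was reviewed.

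**The concern.** The Group effect is an observational contrast, so its credibility depends on how confounding is handled. Bias from a variable depends on the size of the gap between groups and on its link with k. A p-value measures neither: with 50 per group, a gap large enough to matter can easily be non-significant, and the variable then stays out of the model. An imbalance in income, education, smoking, age or methadone dose could then be read as an effect of chronic pain, both in the Group effect and in the between-group contrast in withdrawal.

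The rule also makes the primary model data-dependent, and its wording allows two models. Either only the variables that differ significantly enter, or all five enter once any test is significant.

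**Working it through.** **The plan's own figure.** Inputs from the synopsis and section 14.6: 100 analysed (50 per group), two-sided alpha 0.05, correlation 0.5 between the two sessions, between-group f² = 0.08. The noncentrality for Group is 0.08 × 100 × 2 / (1 + 0.5) = 10.67 on 1 and 98 df, which gives power of 89.9%. The stated power above 80% is therefore reproduced for Group. In SD units the planned difference is 2 × √0.08 = 0.566.

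**What the baseline tests can see** (level not stated; 0.05 two-sided assumed).
- Smallest significant observed gap: t(0.975, 98) × √(2/50) = 1.984 × 0.2 = 0.397 SD.
- Probability that one test misses a true gap (noncentral t): 0.832 at 0.2 SD and 0.682 at 0.3 SD.
- Probability that all five independent tests miss: 0.832⁵ = 0.40 and 0.682⁵ = 0.15.
- Probability that at least one is significant when there are no gaps: 1 − 0.95⁵ = 0.226.

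**Effect on the Group estimate.** The documents give no gaps and no covariate links, so these are assumed. Simulation: 6,000 runs, 50 per group, per-session SD of log k equal to 1, correlation 0.5, so the variance of a person's mean is 0.75; five independent covariates. A link is the change in log k, in per-session SDs, per SD of the covariate. There is no true Group effect. Rule A enters only significant variables; rule B enters all five if any test is significant; rule C always enters all five. The unadjusted bias is the sum of gap × link.

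| Scenario (gap, link) | Unadjusted bias | A: bias / type I error | B: bias / type I error |
|---|---|---|---|
| Five, same direction (0.3, 0.2) | 0.30 | 0.131 / 11.1% | 0.027 / 7.4% |
| Five, same direction (0.2, 0.2) | 0.20 | 0.114 / 8.5% | 0.054 / 6.8% |
| Five, same direction (0.1, 0.2) | 0.10 | 0.069 / 6.3% | 0.050 / 5.9% |
| Five, same direction (0.3, 0.1) | 0.15 | 0.067 / 6.7% | 0.014 / 5.5% |
| Five, same direction (0.2, 0.1) | 0.10 | 0.060 / 5.8% | 0.029 / 5.5% |
| Three against two (0.3, 0.2) | 0.06 | 0.026 / 4.8% | 0.006 / 5.2% |
| Three against two (0.2, 0.2) | 0.04 | 0.023 / 4.4% | 0.012 / 4.4% |
| One confounder (0.3, 0.2) | 0.06 | 0.028 / 5.4% | 0.024 / 5.4% |
| Two confounders (0.3, 0.2) | 0.12 | 0.054 / 5.8% | 0.032 / 5.6% |

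Rule C gave −0.003 / 5.3% in the first row and −0.001 / 4.3% in the second; overall its bias was 0.00 and its error 4 to 6%.

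A separate simulation of 5,000 runs per scenario took one or two confounders with gaps of 0.2 to 0.4 and links of 0.2 to 0.3. Bias was 0.020 to 0.082 SD under A, 0.016 to 0.049 under B and −0.004 to 0.003 under C. Type I error was 4.4 to 7.0% under A and B and 4.6 to 5.3% under C.

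**Precision of the Group effect, no gaps, true difference 0.566 SD.**
- Links of 0.2 (5 × 0.04 / 0.75 = 27% of person-mean variance explained): standard error 0.173 (A), 0.169 (B), 0.152 (C); power 0.903, 0.913, 0.956.
- Covariates unrelated to k: standard error 0.174, 0.175, 0.177; power 0.900, 0.899, 0.889.

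**The case against.** The strongest reply is about size. The text says that matching variables will be included, not that those which differ will be, so rule B is the more natural reading. Under B the worst simulated bias is 0.054 SD, below 10% of the planned 0.566 SD, with type I error of at most 7.4%. The 0.13 SD and 11% figures need rule A and all five variables confounding in one direction, which means recruitment matching has failed on every variable at once.

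The rule is also far better than no adjustment. In the same-direction rows with gaps of 0.2 or 0.3, B removes about 71 to 91% of the unadjusted bias and A about 40 to 56%. Effective matching would also lower the 23%. If it induced a between-group pair correlation of 0.3 or 0.5 on each variable (an assumption), each test would be significant in about 1.9% or 0.6% of trials, and at least one of five in about 9% or 3%. The promised SAP could still change the rule.

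These points stand as limits on size. They do not justify the trigger. Matching has no stated tolerance and appears only in section 14.2, not in the eligibility criteria, group assignment or Screening visit. Both readings remain open in the text, and section 14.2 is the rule in force until the SAP replaces it. Over-adjustment is not a reason to keep the trigger either, because the plan already chose these five variables for matching and for conditional adjustment.

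**Conclusion.** The concern holds. Baseline significance tests decide confounder control for a non-randomised primary contrast, and nothing else in the documents fixes the adjustment in advance. The probable harm is moderate: near-nominal error in the milder scenarios, and up to 0.13 SD of bias with 11% type I error at the adverse end of the less literal reading. These sizes rest on assumed gaps and links, five independent covariates, a 0.05 baseline level and no explicit model of matching. The zero bias under constant adjustment holds because the simulations contain no other confounders.

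The scope is the Group main effect and the PAIN versus NO PAIN contrast in withdrawal. The within-person Condition effect is not affected, and adding these variables as main effects would not change the Group by Condition estimate in participants who complete both sessions.

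**What to change.** Keep the recruitment matching. In the SAP, enter methadone dose, cigarettes per day, annual income, years of education and age as fixed covariates in the primary PROC MIXED model whatever the baseline p-values. Describe balance with standardised differences, and report the unadjusted model as a sensitivity analysis. State that this removes only measured confounding by these five variables, so the Group effect remains an observational association.

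Section 9.1.2 names only date of birth, gender and race, so confirm that income and education are recorded at Screening, and likewise cigarettes per day, which it does not name either.

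The cost is SAP wording, possibly a few Screening items, and five degrees of freedom. If the variables are unrelated to k, the standard error is about 2% larger than when only significant variables enter (0.174 to 0.177 with no gaps; 0.183 to 0.187 with gaps of 0.3 SD). With gaps of 0.3 SD and links of 0.1 it is 0.181 under all three rules. If the variables explain about 27% of person-mean variance, power rises from about 0.90 to 0.96.

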6.2 Inclusion Criteria

- Male and female adults aged 18-65
- Stable methadone dose (at least 21 days) verified by contacting participant's opioid treatment program
- Understand and speak English
- Urine toxicology screen negative for drugs of abuse and positive for methadone
- Must be without by signs of intoxication as evidenced by ability to receive full dose of methadone prior to research activities

Version #: 1.9 Version Date: 12/09/2020 Page 13 of 37

 Presence of chronic pain (>3 months) for the PAIN group and absence of pain for the NO PAIN group

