7 CONCURRENT MEDICATIONS

All subjects should be maintained on the same dose of methadone throughout participation in the trial.

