8.4.1 Dosage/Dosage Regimen

Naloxone 0.1 mg will be given via IM injection, preferably in the Deltoid region. The total volume will not exceed 0.5 mL per injection. Naloxone is a MOR antagonist that had FDA approval to be used to reverse opioid toxicity and is routinely used in experimental studies to induced mild opioid withdrawal symptoms (Strain et al., 1995, Strain et al., 1992; Mendelson et al., 1997; Kanof et al., 1991). In addition, one pre-clinical study in female stumptailed macaques maintained on morphine showed 0.1 mg naloxone administration elicited behaviors consistent with mild opioid withdrawal (Grant et al., 1988). Normal saline will be used as placebo and will also be administered via IM injection. The total volume of placebo will be equal to naloxone injection, not to exceed 0.5 mL per injection.

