12 DISCONTINUATION AND REPLACEMENT OF SUBJECTS

12.1 Withdrawal of Subjects

A subject may be discontinued from study treatment at any time if the subject or the investigator feels that it is not in the subject's best interest to continue. The following is a list of possible reasons for study treatment discontinuation:

- Subject withdrawal of consent
- Subject is not compliant with study procedures
- Adverse event that in the opinion of the investigator would be in the best interest of the subject to discontinue study treatment
- Recurrent intoxication or + UDS
- Lost to follow-up
- Positive pregnancy test (females)
- Change in methadone dose between Sessions 1 & 2
- +COVID-19 test or inability to enter Ward 95 due to screening positive for COVID-19 symptoms/recent exposure

If a subject is withdrawn from treatment due to an adverse event, the subject will be followed by the Investigator until the abnormal parameter or symptom has resolved or stabilized.

Version #: 1.9 Version Date: 12/09/2020 Page 23 of 37

All subjects are free to withdraw from participation at any time, for any reason, specified or unspecified, and without prejudice.

Reasonable attempts will be made by the investigator to provide a reason for subject withdrawals. The reason for the subject's withdrawal from the study will be specified in the subject's source documents.

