14.5 Interim Analysis

Researchers will look at the data from the first 10 completers. If there is no trend of differences in delay discounting between placebo and naloxone administration sessions, we would discuss with our NIDA program official and independent medical monitor ([name]) on the following two options: increasing the dose of naloxone to 0.15 mg or administering 0.1 mg naloxone at trough instead of peak methadone levels.

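### The planned methadone-dose covariate cannot adjust the Group x Condition interaction, so any PAIN versus NO PAIN difference in effective naloxone challenge stays in it

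*Combined protocol and SAP*

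**What the plan says.** All references are to the combined protocol and SAP.

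- **Challenge.** Section 8.4.1: "Naloxone 0.1 mg will be given via IM injection, preferably in the Deltoid region". The two interim options in 14.5 are "increasing the dose of naloxone to 0.15 mg or administering 0.1 mg naloxone at trough instead of peak methadone levels"; neither scales the challenge to a participant's own methadone dose.
- **Methadone at entry.** Section 6.2 requires "Stable methadone dose (at least 21 days) verified by contacting participant's opioid treatment program". It gives no minimum, maximum or stratum.
- **Methadone during the study.** Section 7: "All subjects should be maintained on the same dose of methadone throughout participation in the trial". Section 12.1 lists "Change in methadone dose between Sessions 1 & 2" among the reasons for discontinuation.
- **Balance between groups.** Section 14.2 makes methadone dose one of five matching variables, to be matched by effort during recruitment, and concedes that this is weaker than formal matching. The groups are then tested, and if they differ significantly, "matching variables will be included as covariates in subsequent analyses". No covariate-by-Condition term is named.
- **Model.** Section 14.3 fits Group, Condition and their interaction in PROC MIXED: "The Group x Condition interaction will be examined to determine if group differences vary by condition". Planned contrast 1 compares withdrawal with control within PAIN. Planned contrast 2 compares PAIN with NO PAIN in withdrawal.
- **Data set and power.** Section 14.1 specifies a completer analysis. The synopsis claims more than 80% power for Group, Condition and the interaction.
- **Related checks.** Section 14.2 looks at the 15-minute withdrawal measures for group comparability. Section 14.3 adds a naloxone-session analysis that includes peak COWS.

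**The concern.** PAIN and NO PAIN are observed groups. Randomising session order does nothing to balance methadone dose between them. If the groups differ in methadone dose, and if the response to a fixed naloxone dose depends on methadone dose, the two groups receive a different effective challenge. The resulting difference in within-person change appears in Group x Condition. It could be read as chronic pain amplifying the effect of withdrawal, or it could hide such an effect.

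The covariate in 14.2 is the analytic backstop for failed matching. For this one estimate it has no effect, so a reader who sees a methadone-adjusted model could wrongly take the interaction to be adjusted.

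**Working it through.** **1. The plan's own power figure.** Inputs from the synopsis and 14.6: N = 100, two sessions, correlation 0.5, f² = .02 within subjects and .08 between groups, two-sided alpha .05. The f² = .02 is applied to the interaction as well, since no separate value is given.

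- Group: λ = 0.08 × 100 × 2 / (1 + 0.5) = 10.67; power 89.9% (noncentral F, 1 and 98 df).
- Condition and Group x Condition: λ = 0.02 × 100 × 2 / (1 − 0.5) = 8.0; power 79.97% by noncentral F, 80.7% by normal approximation.

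The claim is reproduced to within rounding, but the interaction sits at 80% with no reserve. The effect it is powered for is a difference in differences of 4 × √.02 = 0.566 SD.

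**2. Why the covariate cancels.** Let participant i have dose Xᵢ in both sessions and a main-effect coefficient β. The between-session change is

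(withdrawal + βXᵢ) − (control + βXᵢ) = withdrawal − control.

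With both sessions present, Group x Condition is the group difference in mean change, so β drops out.

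**3. Numerical check.** One simulated trial: 50 per group, complete pairs, dose imbalance 0.5 SD, no true interaction.

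| Model | PAIN − NO PAIN, control | PAIN − NO PAIN, withdrawal (contrast 2) | Group x Condition |
|---|---|---|---|
| No covariate | 0.212 | 0.196 | −0.016 |
| Dose as main effect | 0.136 | 0.120 | −0.016 |
| Dose x Condition | 0.097 | 0.159 | 0.062 |

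The main effect shifts both group differences by the same 0.076, so their difference does not move. Over 40 simulated trials the largest change in the Condition or interaction estimate was 6e-15. The identity also held under an unequal-variance unstructured covariance. A single draw shows only which estimates move, not that bias has been removed; step 5 addresses bias.

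**4. Average Condition effect.** Averaged over the two equal groups it is 0.3379 − 0.0162/2 = 0.3298 without the covariate and 0.2988 + 0.0620/2 = 0.3298 with dose x Condition. It is unchanged.

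**5. Size of the bias.** The documents give no dose distribution and no effect of dose on response, so these are assumptions: imbalance 0.2 to 0.8 SD, and a slope of 0.1 to 0.4 SD of log k in the withdrawal effect per SD of dose. The bias is imbalance × slope:

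- smallest: 0.2 × 0.1 = 0.02 SD;
- largest: 0.8 × 0.4 = 0.32 SD;
- at 0.4 SD imbalance: 0.04 to 0.16 SD, which is 7% to 28% of the 0.566 SD the plan is powered for.

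False-positive rate for Group x Condition (20,000 replicates per cell, nominal 5%):

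| Imbalance | Planned model, slope 0.1 | Planned model, slope 0.4 |
|---|---|---|
| 0.2 SD | 5.3% | 6.4% |
| 0.4 SD | 5.3% | 11.3% |
| 0.6 SD | 6.0% | 19.6% |
| 0.8 SD | 7.0% | 31.4% |

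With dose x Condition in the model the mean bias is about 0 and the rate is 4.7% to 5.2% throughout.

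**6. What the baseline test lets through.** At 50 per group the observed difference becomes significant at t(.975, 98) × √(2/50) = 1.984 × 0.2 = 0.397 SD. A smaller difference triggers no adjustment. A larger one triggers an adjustment that leaves the interaction as it was.

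**7. Cost of the extra term.** If dose does not predict the change, the standard error grows by √(1 + imbalance² × 50 / (2 × 98)). That is 1.005 at 0.2 SD, 1.020 at 0.4 SD and 1.079 at 0.8 SD. By normal approximation, power goes from Φ(2.828 − 1.960) = 80.7% to Φ(2.828/1.020 − 1.960) = 79% at 0.4 SD, and to Φ(2.828/1.079 − 1.960) = 75% at 0.8 SD.

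**The case against.** Several points on the other side stand.

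- **Matching is the main safeguard.** A reader might infer that the covariate is the plan's only protection. It is not: 14.2 commits real effort to matching on methadone dose, and if that succeeds there is no bias.
- **Condition is not at risk.** A reader might infer that the withdrawal effect itself is compromised. Condition is compared within person with sessions in random order, so a group imbalance cannot confound its average, and the proposed term leaves that average unchanged (step 4). Contrast 1 is also untouched by the covariate, but it lies within PAIN and so is not confounded by group imbalance.
- **The covariate is not useless.** It adjusts the Group effect and moves contrast 2, which also depends on the challenge. In a naloxone-session-only analysis, with one observation per person, it would not cancel.
- **The interaction is not a named primary hypothesis.** Section 14.3 names the Group and Condition effects; the interaction is examined. It is nonetheless in the primary model and carries a power claim.
- **The 14.5 inference is limited.** The trough option suggests that methadone level matters to the response. It concerns timing, and does not show that response differs by maintenance dose among stable patients. Modification by dose is plausible, not established.
- **The wording is open, and section 14 promises a SAP.** A later SAP could add the product term. But 14.4 names an interaction where one is wanted (Condition by PCS), and none is named for methadone.

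The withdrawal-measure comparison and the peak COWS analysis could reveal a difference in challenge, but neither adjusts the interaction. Keeping one-session participants does not rescue the covariate either: with 65 per group and 25% missing a session, the interaction moved only by chance (mean 0.001, SD 0.010).

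**Conclusion.** The point holds for Group x Condition. The invariance is exact for participants with both sessions, which is the planned completer set, given that methadone dose is constant across sessions and that the covariate enters as a main effect.

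The size is conditional. It needs both a residual dose imbalance and a dependence of the naloxone response on dose; if either is absent there is no bias. Over the assumed ranges the bias is 0.02 to 0.32 SD, and the upper end, with a false-positive rate above 30%, needs a 0.8 SD imbalance. Around the test threshold the inflation is modest to moderate. A reader might infer from the figures that the groups will differ or that the interaction will be wrong; the documents give no dose data that would support either, nor the direction of any bias.

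This is an inexpensive improvement worth making before the analysis is fixed, not a flaw in the study's main comparisons.

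**What to change.** In 14.3 or the SAP, prespecify centred methadone dose (as verified at entry) and methadone dose x Condition in the PROC MIXED model, regardless of the baseline test. Report Group x Condition from that model, with the estimate without methadone terms as a sensitivity analysis, and show peak COWS by group beside it so that achieved withdrawal can be compared directly.

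This takes about one sentence, uses data the study already needs for matching, and requires no change to dosing. The price is two model degrees of freedom and, if dose is imbalanced but does not predict the change, an interaction standard error up to about 8% wider in the scenarios examined. That matters somewhat because power for this test is already only about 80%. If dose does predict the change, the term recovers some or all of that precision.
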